#### 4.1.1. Baseline and Handling Missing Data

All summaries and analyses will be based on observed data and missing data imputation is not planned.

#### 4.2. Analysis of Primary Endpoints

Below is a description of the analyses performed to address the study objectives and to analyze the corresponding endpoints.

*Measure the effect of PT on physical function using digital measures from wearable sensors*

The following analyses will be performed to address this primary aim.

- A. Validate wearable sensor-based metrics of functional biomechanical tests in people with knee OA against optical motion capture

Wearable sensor metrics (Gait: Table 1 rows *a.* – *n.*; Sit-to-stand: Table 2 rows *a.* – *d.*) will be compared against the same measures obtained from the optical motion capture system (used as the gold-standard) using intra-class correlation coefficient (ICC) and its 95% lower and upper confidence limits. The ICC reflects both the degree of correlation and agreement between the measurements. We will interpret agreement between measurements according to the following benchmarks:  $ICC \leq 0.4$  indicates ‘poor’, 0.4 to 0.59 ‘moderate’, 0.6 to 0.74 ‘good’, and 0.75 to 1 ‘excellent’ reliability. In addition, we will also compute the mean, variance and percentage error between the standard and the digital measurements. Bland–Altman plots and 95% limits of agreement (average difference  $\pm 1.96$  standard deviation of the difference) will also be computed.

- B. Compare wearable sensor-based metrics of physical performance in people with knee OA with standardized physical performance outcomes.

Wearable sensors metrics showing excellent reliability from analysis A will be examined (i.e. a subset of the metrics shown in Table 1 rows *a.* – *n.* for Gait; and Table 2 rows *a.* – *d.* for Sit-to-stand). Sensor-based metrics will be derived during physical performance tests conducted in-lab and will be correlated with the corresponding standardized physical performance outcomes using Pearson’s product-moment correlations or Spearman’s rank order correlations depending on their normality.

Specifically, the comparisons that will be computed are shown in Table 5.

**Table 5. Comparisons of sensor-based metrics of physical performance with standardized physical performance outcomes**

Task	Standardized Physical Performance Outcomes	Wearable Sensor Metrics
5 times sit-to-stand	Time taken to complete 5 chair stands	Subset of reliable metrics from Table 2 rows a. – d.

6 minute walk test	Distance covered (m)	Subset of reliable metrics from Table 1 rows a. – n .
SPPB	Gait speed score, Repeated chair test score	Subset of reliable metrics from Table 1 rows a. – n . for Gait; and Table 2 rows a. – d . for Sit-to-stand).

C. Assess the effects of exercise-based PT on outcomes from wearable sensors during in-lab physical performance tests

Wearable sensors with excellent reliability from analysis A will be examined (i.e. a subset of the metrics shown in Table 1 rows *a.* – *n*. for Gait; and Table 2 rows *a.* – *d*. for Sit-to-stand). Mixed model repeated measures (MMRM) analysis will be used to investigate the effect of PT on endpoints derived from the lumbar sensor during in-lab physical performance tests (5 times sit-to-stand, 6 minute walk test, SPPB). The outcome measures will be expressed as the change from baseline at each visit (i.e. 6 and 12 weeks). The model will include the baseline value of the outcome variable, week (as a categorical factor), and the interaction between the baseline value and week, as well as covariates such as age, sex, BMI, and presence of comorbidities. Unstructured covariance matrix will be assumed for the model errors, unless additional structure is required for convergence. If visual inspection of the model diagnostics (i.e. residuals) suggest that a transformation of the endpoint should be performed, this will be applied as appropriate prior to analysis (i.e. change from baseline would be calculated on the transformed scale) and documented in the final report as required. The Least Squares Means (LSMeans) together with 95% confidence intervals will be obtained for each visit and plots will be produced illustrating the trajectory of the LSMeans over time. The above outputs will be back-transformed to the original scale for transformed endpoints as required. Missing values will be accounted for by utilizing a maximum likelihood-based approach as part of the MMRM assumptions.

The primary analyses will be applied to each endpoint separately.

Sensitivity analyses will include (a) only in participants who attended at least 80% (14 visits) of the PT visits, and (b) in all participants stratified into < 6 PT visits attended, 6-12 PT visits attended, and >12 PT visits attended.

D. Assess the effects of exercise-based PT on outcomes from wearable sensors collected at-home

The following definitions will be used for analysis of at home sensor data. Based on the literature, a recording day will be considered valid and included in the analysis if it contains at least 10 waking hours (identified using the Cole-Kripke algorithm implemented in ActiLife software) of wear-time. At-home wrist and lumbar sensor data will be summarized on a weekly basis. A week of recording will be included in the analysis if there is at least 4 valid days (as described above) in a 7-day period.

A subset of wearable sensor metrics for gait and sit-to-stand from Section 3.1. E. that are shown to have excellent reliability from analysis A, and the physical activity measures from Actigraph (Section 3.1. E) will be examined. Since *number of gait bouts* derived from free living data is not assessed in

the lab, this will be automatically included in this analysis. The same MMRM approach and sensitivity analyses described above will be used to investigate change from baseline to 6- and 12-weeks with PT on at home sensor endpoints. Mean/median for each endpoint (depending on the distribution of the endpoint) across a valid period will be used in the analyses.

E. Assess the effects of exercise-based PT in-lab tests of physical performance.

The same MMRM approach and sensitivity analyses described above will be used to investigate change from baseline to 6- and 12-weeks with PT on all physical performance outcomes described in Section 3.1. D.

F. Assess the effects of exercise-based PT using joint mechanics during in-lab functional biomechanical tests

The same MMRM approach and sensitivity analyses described above will be used to investigate change from baseline to 6- and 12-weeks with PT on all endpoints derived from optical motion capture system (Gait: Table 1. Column 2; Sit-to-stand: Table 2. Column 2; Section 3.1. C) during in-lab visits.

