5.1. Inclusion Criteria

- Male or female of any race, ≥ 50 years of age.
- A confirmed clinical diagnosis of osteoarthritis of the knee based on American College of Rheumatology criteria (confirmed by the participants' attending physician).

- Score ≥ 3 on weight-bearing questions from the Knee injury and Osteoarthritis Outcome Score (KOOS) Pain Subscale in the index knee
- BMI ≤ 40 kg/m²
- Able to walk without assisted devices (eg, cane or walker) for at least 20 minutes
- Can speak and understand English at a sufficient level to understand the study procedures and informed consent.
- Available for the study duration

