Peak sagittal trunk angle (deg)
Peak medial quadriceps-medial hamstrings co-contraction
Peak knee adduction moment (%BodyWeight x Height)
Peak knee flexion moment (%BodyWeight x Height)
Peak knee flexion (deg)
Balance Measures
Center of pressure displacement in A-P direction (mm)
Center of pressure displacement in M-L direction (mm)
Mean center of pressure velocity (mm/s)

Strength Assessment

Participants' strength will be evaluated with an isokinetic dynamometer through tasks of knee flexion and extension on the side of the index joint. Tests include maximal isometric extension torque (x3), maximal isometric flexion torque (x3), isokinetic flexion-extension at 60 deg/s (x2), and isokinetic flexion-extension at 120 deg/s (x2). Additionally, isometric plantarflexion trials (x2) will be recorded for the purpose of EMG normalization.

Device to be used: Biodex System 3

Raw Data obtained:

- Torque
- Angular position
- Angular velocity

Derived measures:

- Isometric testing
 - Peak extensor torque (Nm/kg)
 - Peak flexor torque (Nm/kg)
- Isokinetic testing
 - Peak extensor torque at 60 deg/s (Nm/kg)
 - Peak flexor torque at 60 deg/s (Nm/kg)
 - Peak extensor torque at 120 deg/s (Nm/kg)
 - Peak flexor torque at 120 deg/s (Nm/kg)

In-lab Functional Assessments (only wrist and lumbar sensors will be worn during these tests):

- *Stair climbing test (SCT)*
 - Ascending and descending a flight of stairs (x2)
 - Will only be assessed during in-lab visits

- **6-minute walk test (6MWT)**
 - Distance covered in 6 minutes
 - Will only be assessed during in-lab visits
- **15-second step-up test:**
 - Number of step-ups in 15-second (4in step)
 - Will be assessed during both in-lab and at-home visits
- **7-meter gait test**
 - Get up from a chair, walk 7 meters, turn around, return to starting position, sit down
 - Will be assessed during both in-lab and at-home visits
- **Short Physical Performance Battery (SPPB).** SPPB includes the following tests
 - Balance tests (all performed with eyes open and under close supervision of a study staff member)
 - Side-by-side stand – standing with feet side-by-side for 10 seconds
 - Semi-tandem stand – standing with side of the heel of 1 foot touching the big toe of the other foot for 10 seconds
 - Tandem stand – standing with the heel of one foot in front of and touching the toes of the other foot for 10 seconds
 - Will only be assessed during in-lab visits
 - Gait speed test (x2)
 - walking over a 4-meter walkway

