 - Will only be assessed during in-lab visits
 - Single chair stand
 - Will only be assessed during in-lab visits
 - Repeated chair stands i.e., 5 chair stands (x2)
 - Will only be assessed during both in-lab and at-home visits

Functional Assessment	Clinical Metric	Lumbar Sensor Measures	3-sensor inertial system
Stair Climb Test	Time to complete (sec)	NA	NA
15-second step-up test	Number of step-ups	NA	NA
6-minute walk test	Total distance traveled (meters)	Metrics will be calculated with in-house algorithms	Same metrics as lumbar sensor
7-meter gait test	NA	Metrics will be calculated with in-house algorithms	Same metrics as lumbar sensor
SPPB	Total balance test score Gait speed test score Chair stand test score Total score	Metrics will be calculated with in-house algorithms	Same metrics as lumbar sensor

6.1.2 In-Lab Pain Phenotype Assessments:

Quantitative Sensory Testing (QST) and Exercise-Induced Hypoalgesia (EIH)

Devices to be used: Medoc AS00301 AlgoMed Computerized Algometry System; von Frey monofilament set, Blood pressure cuff.

The QST is a valuable method for evaluating pain sensitization by examining the nociceptive response after application of different painful stimuli of controlled intensity to assess the function of both large and small nerve fibers and its central pathways.

Raw Data obtained:

- Pressure pain threshold (PPT): at the index knee joint and a wrist joint (in kgf)

Tasks to be performed:

- **PPT:** refers to the pressure at which the person first notes the pressure changing to slight pain. The pressure is applied using a hand-held algometer at the index knee and an uninvolving wrist (control site). PPT assessed at a site of disease (e.g., knee with OA) is a reflection of peripheral +/- central sensitization, whereas when it is assessed at an otherwise undiseased site (e.g., wrist as the referent site), it is a reflection of central sensitization. Three trials are performed at each site and the average of the last two trials is used in the analysis. Lower scores indicate greater “pressure pain sensitivity”. The outcome is the mean PPT (in kgf) across the three trials.

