**D. In-lab Data: Physical Performance Outcomes**

- 5 times sit to stand
  - Time taken to complete 5 chair stands
- 15 second step up test
  - Number of step ups with each foot in 15 seconds
- Stair climbing test
  - Time taken to complete (sec)
- 6 minute walk test
  - Distance covered (m)
- Short Performance Physical Battery
  - Total score
  - Gait speed score
  - Repeated chair stand score
  - Balance tests score

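### In Analysis B the SPPB walk enters SAP Table 5 only as a graded gait speed score; adding the 4-meter time or speed behind it would give a less attenuated correlation

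*SAP*

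**What the plan says.** SAP 4.2, Analysis B, takes the sensor metrics that reached excellent agreement in Analysis A. It derives them during the in-lab performance tests, and they are then "correlated with the corresponding standardized physical performance outcomes". Pearson or Spearman is chosen according to normality, which SAP 4.1 assesses with the Shapiro-Wilk test.

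Table 5 has three rows:

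- **5 times sit-to-stand:** the comparator is the time for five chair stands.
- **6-minute walk test:** the comparator is the distance in meters.
- **SPPB:** the comparators are "Gait speed score, Repeated chair test score".

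SAP 3.1 D likewise lists "Time taken to complete 5 chair stands" as an outcome apart from the SPPB scores. For the SPPB walk it lists only "Gait speed score". The functional assessment table in Protocol 6.1.1 does the same, with "Gait speed test score". The same protocol section describes the test itself as "walking over a 4-meter walkway", done twice. Neither document names the time or speed of that walk as an outcome or comparator, and neither explains why the score is used alone.

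**The concern.** The SPPB gait component and the sensor's gait speed describe the same walk. Replacing the walk time by a score with few levels discards part of the variation that the sensor is meant to track. The correlation with the sensor then falls even if the sensor is accurate.

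The plan also treats two parts of the same battery differently: the chair test is represented by time and score, the walk by score alone.

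The loss would be large if many participants share the top score. That is plausible here, because entry requires participants to be "Able to walk without assisted devices (eg, cane or walker) for at least 20 minutes". At stake is how the SPPB row reads in an analysis that belongs to the primary aim.

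**Working it through.** **Plan's own figure.** The documents give no expected correlation, threshold or power for Analysis B, so there is nothing to reproduce. From the documents I use only the planned sample size of 60.

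**Assumptions.**

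- Sensor metric and walk time (or speed) are bivariate normal with correlation r = 0.90 in absolute value.
- The score has four ordered levels, coded 0 to 3.
- A share *p* of participants has the top score, and the rest are split equally over the three lower levels.

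That the score is graded is itself inferred: it is listed beside the balance, chair and total scores, and the documents print no bands.

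**Pearson.** For cut-points c₁, c₂, c₃ on the standard normal scale,

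r(score) = r × [φ(c₁) + φ(c₂) + φ(c₃)] / SD(score).

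Example with p = 50%:

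- The cumulative shares at the cut-points are 1/6, 1/3 and 1/2.
- The densities sum to 0.2499 + 0.3636 + 0.3989 = 1.0124.
- The mean score is (0 + 1 + 2)/6 + 3/2 = 2.0.
- The mean square is (0 + 1 + 4)/6 + 9/2 = 5.333.
- SD = √(5.333 − 4) = 1.1547.
- The multiplier is 1.0124 / 1.1547 = 0.877, so r(score) = 0.90 × 0.877 = 0.79.

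**Spearman.** Without grouping it is (6/π) × arcsin(0.90/2) = 0.89. With grouping I simulated 1,000,000 pairs.

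| Share at top score | Multiplier (Pearson) | Pearson | Spearman |
|---|---|---|---|
| ungrouped | 1 | 0.90 | 0.89 |
| 25% | 1.0345/1.1180 = 0.925 | 0.83 | 0.86 |
| 50% | 1.0124/1.1547 = 0.877 | 0.79 | 0.82 |
| 70% | 0.8032/1.0198 = 0.788 | 0.71 | 0.72 |
| 85% | 0.5118/0.7810 = 0.655 | 0.59 | 0.57 |

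The Pearson multiplier does not depend on r. With r = 0.70 the four Pearson values are 0.65, 0.61, 0.55 and 0.46.

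An uneven split of the lower levels (10%, 25% and 65% of the remainder) moved Pearson by less than 0.01 and Spearman by less than 0.03. The share at the top is what matters most.

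**Against sampling error.** The Fisher interval at n = 60 is tanh(atanh r ± 1.96/√57), which is only approximate for a graded score.

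| r | 95% CI |
|---|---|
| 0.90 | 0.84 to 0.94 |
| 0.83 | 0.73 to 0.90 |
| 0.71 | 0.56 to 0.82 |
| 0.59 | 0.40 to 0.73 |

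With 25% at the top the interval overlaps the ungrouped one. With 70% or 85% it does not.

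**The case against.** There are four good arguments for the plan as it stands.

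1. **Gait already has a continuous comparator.** A reader might infer that gait metrics are checked against nothing but a coarse score. Table 5 does not support that. It also pairs them with 6-minute walk distance, with the sensor worn during that same test, and distance over 360 s is an average walking speed. This stands.

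2. **A sound sensor cannot be lost this way.** A reader might infer that a good metric could be rejected. Analysis A compares sensor gait speed with motion-capture gait speed by ICC and Bland–Altman limits, and only metrics rated excellent there enter B. Analyses C and D and the secondary and exploratory aims select on Analysis A and, where stated, on significant change. None selects on B. This stands.

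3. **The score has a purpose.** A reader might infer that using it brings no benefit. Analysis B is meant to relate sensor metrics to standardized outcomes, and the score is what both documents define as the SPPB gait outcome. This stands too. It argues for keeping the score, not for leaving out the time.

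4. **The size is uncertain.** The bands and the score distribution are unknown, and r = 0.90 would be optimistic for many gait metrics. The 20-minute criterion concerns duration rather than speed, and the required weight-bearing pain works against a ceiling. A score with few values would probably fail the Shapiro-Wilk test. Spearman would then apply, and with 25% at the top it drops only from 0.89 to 0.86. So a ceiling is plausible but not shown, and the lower rows of the table are conditional on one.

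What remains is the direction of the effect, and the fact that the walk lacks the treatment that the chair stand receives.

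**Conclusion.** The point holds as a minor improvement, not as an error in the plan. Provided the score is graded, as its listing implies, it gives a weaker correlation than the time or speed behind it, and switching to Spearman does not remove the loss.

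Under the stated assumptions the Pearson loss runs from about 7% for a well-spread score to about 34% with 85% at the top. A loss of the first size would hardly alter the conclusion at n = 60; one of the second size would. The documents do not show where in this range the trial will fall.

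The effect is confined to the SPPB gait comparison in Analysis B. The selection of metrics and the sample size are untouched.

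**What to change.** In the SPPB row of Table 5, add the 4-meter walk time or speed as the main gait comparator. Keep the gait speed score and the repeated chair score as supportive comparisons. Add a matching entry to SAP 3.1 D, and say there how the two walks are combined, since the documents do not.

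The cost is one more set of correlations, at most 14 (Table 1 rows *a* to *n*), within the false discovery rate correction already planned in SAP 4.1. No new test is needed, because the walk is already performed. The recorded time must be kept in the data set along with the score.

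One side effect needs a decision: Analysis E models every outcome in 3.1 D. The new entry should therefore state whether it is for Analysis B only or is also to be modelled for change from baseline.

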5. STUDY POPULATION

The target population will be people with pain due to knee osteoarthritis.

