## 4. ANALYSES AND SUMMARIES

### 4.1. General Methods

Data will be summarized using descriptive statistics (number of subjects (n), mean, median, standard deviation, minimum and maximum) for continuous (or near continuous) variables, and using frequency and percentages for discrete variables. Shapiro-Wilk test will be used to assess normality of variables. Non-parametric statistical methods will be used to analyze non-normally distributed variables.

P-values will be generated where appropriate and any p-value < 0.05 will be considered statistically significant. If multiple p-values are generated within an analyses, Benjamini-Hochberg false discovery rate (FDR) correction will be used to determine significance. P-values will be rounded to 3

decimal places and therefore presented as 0.xxx; P-values smaller than 0.001 will be reported as ‘<0.001’.

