#### 4.3. Analysis of Secondary Endpoint(s)

##### **Secondary Aim 1: Compare in-lab and real world (at-home) sensor metrics with ePRO outcomes**

A. Compare change in in-lab wearable sensor metrics with ePRO outcomes

The change from baseline in ePRO measures from Section 3.2 will be calculated using the same MMRM approach detailed in Section 4.2 C. ePRO measures that show a significant change from baseline to 12-weeks will be examined for this analysis.

Wearable sensor metrics showing a significant change from baseline to 12-weeks during in-lab physical performance tests will be examined (this is the outcome of analysis performed in Section 4.2. C).

The change from baseline to week 12 in these metrics will be correlated with change from baseline in ePRO outcomes using Pearson's product-moment correlations or Spearman's rank order correlations depending on their normality.

Sensitivity analyses will be conducted to estimate the correlation between wearable sensor metrics and ePRO outcomes in (a) responders and (b) non-responders. Responders are defined as participants with  $\geq 50\%$  reduction in KOOS-derived WOMAC 3.0 pain score.

B. Compare change in at-home wearable sensor metrics with ePRO outcomes

ePRO measures from Section 3.2 that show a significant change from baseline to 12-weeks will be examined (as determined by analyses in Section 4.3 A). Wearable sensors metrics which show a significant change from baseline to week 12 during at-home wear will be examined (the outcome of analysis performed in Section 4.2. D).

Change from baseline to week 12 in these sensor metrics will be correlated with change in ePRO outcomes using Pearson's product-moment correlations or Spearman's rank order correlations depending on their normality.

Sensitivity analyses will be conducted to estimate the correlation between wearable sensor metrics and ePRO outcomes in (a) responders and (b) non-responders. Responders are defined as participants with  $\geq 50\%$  reduction in KOOS-derived WOMAC 3.0 pain score.

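### Single-arm MMRM of change: the LSMeans have no stated target, reference values or factor weights, and at sample covariate means their CIs are too narrow for the population mean change

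*SAP*

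**What the plan says.** SAP section 4.2 C, like protocol section 7.1 C, models change from baseline at weeks 6 and 12 in one arm. "The model will include the baseline value of the outcome variable, week (as a categorical factor), and the interaction between the baseline value" and week, together with "covariates such as age, sex, BMI, and presence of comorbidities". The output is specified as: "The Least Squares Means (LSMeans) together with 95% confidence intervals will be obtained for each visit". Neither document gives the covariate values at which the LSMeans are taken, the weights for the levels of sex and comorbidity, or the quantity being estimated.

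The model is reused. For analyses D, E and F: "The same MMRM approach and sensitivity analyses described above will be used to investigate change from baseline to 6- and 12-weeks with PT". For the patient-reported outcomes: "The change from baseline in ePRO measures from Section 3.2 will be calculated using the same MMRM approach detailed in Section 4.2 C". The sleep analysis uses it too, and Secondary Aim 3 uses a similar model with week 18 added. Endpoints with a significant week-12 change go forward to Secondary Aims 1 and 3. On multiplicity, SAP section 4.1 says: "If multiple p-values are generated within an analyses, Benjamini-Hochberg false discovery rate (FDR) correction will be used to determine significance". The same section limits the reach of the model: "Non-parametric statistical methods will be used to analyze non-normally distributed variables". The only statement about a population is in protocol section 5: "The target population will be people with pain due to knee osteoarthritis".

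**The concern.** An LSMean from a model with covariates is undefined until the reference values and weights are fixed, so two analysts can follow the SAP and report different estimates and intervals.

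There is also a problem of precision. In a two-arm comparison the sampling error of the covariate means largely cancels. Here there is one arm and nothing cancels. If change depends on baseline, a sample that happens to start worse than the population will tend to improve more. The model SE at the sample means does not count that variation, so chance regression to the mean can pass as an effect of PT. The intervals for the primary aim, and the tests that select endpoints for the secondary aims, would then be anti-conservative for the mean change in the population.

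**Working it through.** **Inputs from the documents.** Single arm, 60 participants, 10% attrition, two-sided 5% (protocol 4.2); model terms (SAP 4.2 C); ICC 0.85 [0.71, 0.92] for gait speed in healthy adults (protocol 6a, substudy sample size). **Assumed.** The target is the population mean change; LSMeans are taken at sample covariate means; the LSMean test decides which change is significant (the SAP does not name the test); the ICC stands in for the baseline to week-12 correlation r, with equal SDs.

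**1. The plan's own figure.** A paired t-test with effect size 0.40, two-sided 5% and 80% power needs n = 52 (exact power 80.8%), as stated. 52 × 1.1 = 57.2 gives the stated 57 (52/0.9 = 57.8 would give 58). The paired SE, sqrt(Var(change)/n), already contains the variation due to covariates.

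**2. SE deficit.** At the sample covariate means the model variance of the LSMean is σ²/n, with σ² the residual variance. As an estimate of the population mean change its variance is (σ² + b'Cov(X)b)/n, where b holds the covariate slopes. So SE ratio = sqrt(1 − R²), and actual error = 2·P(Z > 1.96·sqrt(1 − R²)).

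**3. Baseline alone.** With both SDs equal to 1, the slope of change on baseline is r − 1 and Var(change) = 2(1 − r). Hence R² = (1 − r)²/[2(1 − r)] = (1 − r)/2.

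| r | Source | R² | SE ratio | Actual error |
|---|---|---|---|---|
| 0.92 | upper ICC limit | 0.040 | 0.980 | 5.5% |
| 0.85 | ICC | 0.075 | 0.962 | 5.9% |
| 0.71 | lower ICC limit | 0.145 | 0.925 | 7.0% |
| 0.5 | assumed | 0.25 | 0.866 | 9.0% |
| 0.3 | assumed | 0.35 | 0.806 | 11.4% |

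**4. Simulation of the planned MMRM** (60 enrolled, weeks 6 and 12, unstructured covariance, REML, 10% missing at random at week 12). Actual error was 5.9%, 8.5% and 10.9% at r = 0.85, 0.5 and 0.3, and 5.4% when change did not depend on baseline. A paired analysis gave 4.6 to 5.3%. Monte Carlo error is up to 1.0 point.

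**5. Other covariates.** Suppose age and BMI each shift change by 0.3 baseline SD per SD. They add 2 × 0.3² = 0.18 to the variance of change. At r = 0.85 that is 0.18/(0.30 + 0.18) = 37.5% of the total, and simulated error is 12.4%. At r = 0.5 it is 0.18/1.18 = 15%, and error is 11.0%.

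**6. Equal weights for sex and comorbidity.** If neither predicts change, simulated error is 5.7% at r = 0.85 and 7.4% at r = 0.5, slightly lower than at sample means. If one sex makes up 65% and the sex effect is 0.5 SD (both assumed), the estimate shifts from the population mean change by (0.65 − 0.50) × 0.5 = 0.075 SD. Error at r = 0.85 is then 15.0%, against 8.4% at sample means.

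**7. Benjamini-Hochberg at 5%**, illustrated with 18 independent endpoints (14 gait rows of SAP Table 1, 4 sit-to-stand rows of Table 2). With half null and half at a true 0.4 SD effect, the false discovery rate at r = 0.85, 0.5 and 0.3 is 3.0, 5.1 and 6.8% (valid tests: 2.5%). With all null it is 6.9, 15.4 and 23.8% (valid tests: 5.0%).

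**The case against.** The best defence is that LSMeans conditional on the observed covariates are ordinary MMRM practice, and that the interval is correct for that target. The plan never says it wants the population mean change. The one line on the target population opens the eligibility section and is not an estimand, and the paired t-test planning concerns WOMAC scores. This stands to the extent that the fault depends on the target. It does not excuse leaving the target, reference values and weights unstated.

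The second defence is size. At the only documented repeatability the excess is about one percentage point, which the simulation can hardly separate from Monte Carlo error. This also stands. A reader might infer from the larger figures that the planned intervals are badly wrong. The documents do not support that: those figures need assumed low correlations or strong covariate effects, and no R² is given.

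A reader might also infer that selection for the secondary aims is seriously corrupted. With a fair share of true effects it is not, and 18 is not the documented family, because analysis C uses several tests and only metrics that pass the ICC threshold. Nor is equal weighting a safe way out: step 6 shows that it helps only when sex and comorbidity do not predict change.

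**Conclusion.** The concern holds in conditional form. The missing target, reference values and weights are a matter of record. If LSMeans are taken at sample covariate means and read as estimates of the population mean change, the CI is too narrow and the test anti-conservative whenever the covariates explain any of the change. Actual error is about 6% (5.5 to 7.0%) at the documented ICC, used as a proxy, and about 9% or 11% at assumed correlations of 0.5 or 0.3. With R² = 0 there is no deficit.

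The reach is limited. Analyses A and B are unaffected. Secondary Aim 1 is affected only through its significance filter. The week-12 versus week-18 contrast is affected only if covariate slopes differ between those visits. Endpoints sent to non-parametric methods do not use this model, and their number is unknown. For pain scores the eligibility threshold narrows the baseline range and shrinks the term: truncation at the median (assumed) gives 6.4% instead of 9.0% at r = 0.5. This should be fixed, but it does not invalidate the primary analysis.

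**What to change.** State in SAP section 4.2 C that the target is the population mean change from baseline. Then choose one of two routes.

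1. Keep the planned model. Take LSMeans at the sample means of all covariates, with observed proportions for sex and comorbidity, and add b'Cov(X)b/n for all covariates to the squared SE. Correcting for baseline alone is not enough: with the age and BMI effects of step 5 it left 6.7% error at r = 0.5 and 10.8% at r = 0.85.
2. Put baseline in the response vector (baseline, week 6, week 12; week 18 for Secondary Aim 3) with categorical visit and unstructured covariance, and report the week-12 minus baseline contrast.

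If the conditional target is intended, say so, give the reference values and weights, and limit the interpretation to the enrolled sample.

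Cost: the sample size is unchanged. CIs at sample means widen by about 4% at r = 0.85 (1/0.962) and 14 to 15% at r = 0.5 (1/0.866 = 1.155). Route 1 is slightly conservative (about 4 to 4.7% actual error). Route 2 (4.6 to 5.8% in simulation) no longer adjusts the change itself for age, sex, BMI and comorbidity. Protocol section 7.1 C prescribes the same model, and the SAP introduction ties major changes to the primary analysis to a protocol amendment. One may therefore be needed, mainly for route 2.
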